2.2 Secondary Objectives

The secondary objectives of this study are:

- To evaluate the practicality of using CG-SDCT in terms of image quality and artifacts.
- To determine the accuracy of gating, which is measured by the correlation of the between the x-ray pulses and the EKG R-wave within a 30ms window around the x-ray pulse.

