3 INVESTIGATIONAL PLAN

3.1 Study Design

This is a one arm study of 20 patients who have undergone a clinical, outpatient non-contrast CT at UNC Hospitals for any pathological condition of the chest who consent to undergo an experimental s-DCT.

The study scan, s-DCT, will be performed within four weeks of his/her clinical evaluations by chest CT or a TAVR CT. There cannot be any intervening therapies or procedures (i.e. line placement, biopsy or excision of lesions) done in between the CT chest imaging and the s-DCT.

For patients that receive a CT for transcatheter aortic valve replacement (TAVR), this will require an expansion of the field of view from 5cm to 15cm coverage. This group of patients will receive an additional dose of approximately 30 mSv and these patients must be consented to participate prior to receiving their clinical CT.

Images will be acquired by a trained radiology technologist. The scan will consist of the following procedure. First, the patients, will be asked to change into a hospital gown. The technologist will comfortably position the patient in the supine position on the imaging table. EKG leads will be placed in appropriate positions to derive an EKG signal. Once the EKG signal is verified, the R wave will be selected for triggering the x-ray source. The subject will be asked to hold their breath, then the gated scan will be performed in an anterior-posterior direction. We anticipate that a breath hold of approximately 25 to 30 seconds will be required for the subject, with a single image acquired during each R wave. Images will be reconstructed off-line and transferred for review on conventional PACS workstations. Total patient preparation and imaging time should not exceed 20 minutes.

A reader study will be performed after all patients have been accrued. Each of the scans will be de-identified. As reading of all tests will take place after the patient has undergone clinical decision-making (treatment versus following), the results of this study will not affect patient care. Clinical calcium scoring will be performed using conventional software by trained personnel. Calcific lesions in the distribution of the coronary arteries will be identified on tomosynthesis images and a total score also derived. Readers will be blinded to the calcium score from the other modality. Reader confidence in image quality will also be assessed on a 1 to 10 scale.

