6.5 Secondary Analysis

The 30 ms cardiac EKG trace will be extracted for each of the projections. Then, a Pearson correlation coefficient will be calculated for each of the projections relative to the first x-ray projection. The mean of the Pearson of the correlation coefficients will then calculated and served as an estimate of the timing precision of each projection set for each patient. The mean and standard deviation of the correlation coefficients will be reported.

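### The mean Pearson r that section 6.5 calls timing precision is only an uncalibrated index of beat-to-beat jitter: its value depends on where the 30 ms window sits on the R wave, which the plan does not fix, and it cannot show gating accuracy

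*Combined protocol and SAP*

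**What the plan says.** Section 2.2 makes the accuracy of gating a secondary objective, measured by the "correlation of the between the x-ray pulses and the EKG R-wave within a 30ms window around the x-ray pulse". Section 6.5 is the only analysis that serves it. "The 30 ms cardiac EKG trace will be extracted for each of the projections", and then "a Pearson correlation coefficient will be calculated for each of the projections relative to the first x-ray projection". The per-patient average is "served as an estimate of the timing precision of each projection set for each patient". The output is described in one sentence: "The mean and standard deviation of the correlation coefficients will be reported".

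On the trigger, section 3.1 says that "the R wave will be selected for triggering the x-ray source", "with a single image acquired during each R wave". It does not say whether detection is on the upslope or at the peak, or what delay separates detection from the pulse. Section 6.5 describes no lag search or alignment, so the correlation is read here as zero-lag. It gives no conversion to milliseconds and no value of r that would count as accurate gating.

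**The concern.** Pearson r ignores level and scale. If the window lies on a nearly straight flank of the R wave, a snippet taken a few ms later is almost the same line plus a constant, and r stays near 1. If the window straddles the peak, the snippet is roughly symmetric, and the same few ms pull r down sharply. Equal timing error can therefore give very different values of r.

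The objective also concerns accuracy. Comparing each beat with another beat of the same scan shows repeatability at most. Pulses that all arrive late by the same amount still match each other.

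At stake is the interpretation of a named secondary objective in a first-in-human gated scan. A mean r of 0.5 and a mean r of 0.9 could come from the same jitter, and a reader of the results could not tell.

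**Working it through.** The plan states no figure to reproduce, so the statistic was computed as section 6.5 describes it, on assumed waveforms.

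**Inputs from the documents.** Window 30 ms, centred on the pulse (2.2, 6.5); reference is the first projection (6.5); one projection per R wave in a breath hold of about 25 to 30 seconds (3.1).

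**Assumed, because the documents are silent.** Gaussian R wave with SD s = 8, 10, 12 or 15 ms, with or without small Q and S waves; 1 ms sampling; EKG noise of 0 or 2% of R amplitude; about 30 projections; normally distributed jitter.

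**Step 1: one shift, no noise.** Let g(t) = exp(−t²/2s²), with t in ms from the R peak. For a window centred at c and a second beat sampled d ms later,

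r(c, d) = corr{ g(c+u), g(c+d+u) }, u = −15, …, +15 ms.

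For d = 5 ms and s = 10 ms:

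| Window centre | r, no Q/S | r, with Q/S |
|---|---|---|
| R peak | 0.60 | 0.64 |
| 10 ms before | 0.86 | 0.87 |
| 15 ms before | 0.95 | 0.95 |

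Over s = 8 to 15 ms, the ranges are 0.59 to 0.65 at the peak and 0.91 to 0.98 at 15 ms before it. The direction is the same for every width, with or without Q and S.

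**Step 2: the per-patient statistic.** Mean r of projections 2 to 30 against projection 1, with Q and S waves and 2% noise, averaged over 200 simulated scans:

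| Jitter SD, window centre | s = 8 | s = 10 | s = 12 | s = 15 |
|---|---|---|---|---|
| 5 ms, on peak | 0.49 | 0.48 | 0.51 | 0.51 |
| 5 ms, 15 ms before | 0.84 | 0.89 | 0.94 | 0.95 |
| 5 ms, 15 ms after | 0.80 | 0.90 | 0.94 | 0.96 |
| 2 ms, on peak | 0.86 | 0.84 | 0.84 | 0.83 |

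At s = 10 ms, the scan with 2 ms jitter on the peak scores 0.84, while a scan with 5 ms jitter 15 ms off the peak scores 0.89 to 0.90. The order is reversed. A separate run with 29 projections and no noise gives 0.85 against 0.89.

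**Step 3: does r respond to jitter at all?** Yes, at a fixed position. At s = 10 ms without noise, jitter of 2, 5 and 10 ms gives mean r of 0.85, 0.50 and 0.17 on the peak, and 0.99, 0.89 and 0.46 at 15 ms before it.

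**Step 4: constant delay.** If every pulse is late by the same k ms, all snippets are the same stretch of waveform, and r = 1 apart from noise, whatever k is. With jitter present, k changes r only by moving the window along the R wave, as in step 2.

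**Step 5: a measure in ms.** Each trace of ±100 ms was aligned to the patient's mean trace by the lag that maximises cross-correlation. For true jitter of 0, 2, 5 and 10 ms, the SD of these lags averaged 0, 1.8 to 2.0, 4.7 to 5.1 and 9.4 to 10.1 ms, at every window position and R-wave width tried.

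**The case against.** The best defence is that r does track jitter when the window stays put. One prototype with one R-wave trigger may place the window at much the same point in every patient. If that point were always the R peak, R-wave width would hardly matter (0.48 to 0.51 at 5 ms jitter) and patients would be roughly comparable. The reversal in step 2 needs one patient's pulses on the peak and another's about 15 ms away, and the documents give no evidence of differences that large. The summary is descriptive: no planned analysis ranks patients by r, tests it against a threshold or relates it to disagreement with CT.

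Most of this stands, and it limits the point. It does not remove it, because the plan does not fix the window position, and r has no unit even if the position is constant.

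A reader might go further and infer that r says nothing about jitter, or that it can support no statement on precision. Step 3 rules that out: with the window inside the R wave, a high r is evidence against large jitter. A reader might also infer that the window could fall on a flat part of the EKG, where r would be noise even with perfect timing. That conflicts with section 3.1, which places each image during the R wave. Nor do the documents name the R peak as the trigger; they name only the R wave.

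**Conclusion.** The point holds as a specification and labelling weakness. Mean r is an uncalibrated index of jitter. It cannot be read as a time, it is not comparable between patients whose window positions differ, and it cannot show accuracy against the R wave. Under the stated assumptions, 5 ms of jitter gives about 0.5 on the peak and 0.80 to 0.96 at 15 ms off it. The size depends on assumed waveform, noise, sampling and offsets; the direction follows from the definition of r and held for every width tried.

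It would be wrong to infer that patients will in fact be mis-ranked. The documents leave this possible but do not show it. The primary comparison of calcium scores is unaffected, so this is an inexpensive improvement to a secondary analysis.

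**What to change.** In section 6.5:

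- Keep an EKG trace that covers the whole QRS around each pulse, for example ±100 ms.
- For each projection, compute the R-peak-to-pulse delay in ms, or the lag in ms that maximises cross-correlation with the patient's mean QRS.
- Report the within-patient SD of these times as timing precision.
- Report the mean and range of the R-peak-to-pulse delay as gating accuracy. The lag against the patient's own mean cannot serve here, because it misses a constant delay.
- Summarise both over patients.
- If a share within ±15 ms (half of the 30 ms window) is reported, measure it from the R peak. Around the patient's own mean it saturates: with 5 ms jitter, 15/5 = 3 SD, so 99.7% of projections fall inside, and with 2 ms jitter practically all do.
- Mean r may stay as a descriptive figure for waveform similarity, without the precision label.

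The cost is a rewording of 6.5 and slightly more signal processing, with no extra patients or scans. The EKG around each pulse must be kept; the documents mention only a 30 ms trace, so this needs confirming before the first scan. A result in ms may look less favourable than a correlation.

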7 SAFETY MANAGEMENT

7.1 Unanticipated Concerns

7.1.1 Unanticipated Adverse Device Effect (UADE)

The investigational device exemption (IDE) regulations define an unanticipated adverse device effect (UADE) as "any serious adverse effect on health or safety or any life-threatening problem or death caused by, or associated with, a device, if that effect, problem, or death was not previously identified in nature, severity, or degree of incidence in the investigational plan or application (including a supplementary plan or application), or any other unanticipated serious problem associated with a device that relates to the rights, safety, or welfare of subjects" (21 CFR 812.3(s)).

7.1.2 Unanticipated Problems (UP)

As defined by UNC's IRB, unanticipated problems involving risks to study subjects refers to any incident, experience, or outcome that:

- Is unexpected (in terms of nature, severity, or frequency) given (a) the research procedures that are described in the protocol-related documents, such as the IRB-approved research protocol and informed consent document; and (b) the characteristics of the subject population being studied;
- Is related or possibly related to a subject's participation in the research; and
- Suggests that the research places subjects or others at a greater risk of harm (including physical, psychological, economic, or social harm) related to the research than was previously known or recognized.

7.2 Reporting Procedures

7.2.1 UADEs

UADEs must be reported by the clinical investigator to the sponsor and the reviewing IRB, as described below:

For this device study, investigators are required to submit a report of a UADE to the FDA, the manufacturer of the device and the UNC IRB as soon as possible, but in no event later than 10 working days after the investigator first learns of the event (§ 812.150(a)(1)), using the MedWatch Form 3500A. Sponsors must immediately conduct an evaluation of a UADE and must report the results of the evaluation to FDA, the UNC IRB, and participating investigators within 10 working days after the sponsor first receives notice of the effect (§§ 812.46(b), 812.150(b)(1)).

For this device study, we will submit a report of a UADE to the manufacturer and the IRB as soon as possible, but no later than 10 working days after the investigators first learn of the event.

7.2.2 UP

Any events that meet the criteria for "Unanticipated Problems" as defined by UNC's IRB must be reported by the Study Coordinator using the IRB's web-based reporting system.

Any unanticipated problem that occurs during the conduct of this study and that meets at least the first two criteria listed in section 7.1 must be reported to the UNC IRB using the IRB's web-based reporting system.

7.3 Data and Safety Monitoring Plan

All studies will be reviewed within 7 days (time is needed to move and reconstruct the acquired images). If there are concerning lesions or indicator is identified, this information will be communicated to the referring surgeon or the patient's primary physician.

There will not be a Data and Safety Monitoring Board for this study. There will be a non-study related medical monitor, [name] (Vice Chair of Clinical Research, Radiology). The medical monitor will review all Adverse Events (AE) greater than grade 2 with the PI. In addition, he will do an aggregate review of all AEs annually with the PI. In addition, the medical monitor and PI will review all Unanticipated Problems (UP) to determine whether changes are needed to the study protocol or whether the study should end.

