1.3 Name and Description of Investigational Product or Intervention

The stationary digital chest tomosynthesis (s-DCT) system is based on the carbon nanotube (CNT) x-ray source array technology invented by our team at the University of North Carolina. Instead of mechanically moving a large x-generator to different viewing angles for the projection images, s-DCT generates the images by electronically and sequentially

activating the individual x-ray sources inside spatially distributed CNT x-ray source array without moving the source, detector or the patient.

The clinical test ready prototype device will be constructed by combining the commercial digital radiography system detector (Paxscan 4030) with a dedicated CNT x-ray source array (XinRay Systems Inc., NC). An external collimator is connected to the source array to confine the x-ray radiation only to the region of interests to minimize the radiation to the patient and the staff. A computer station (RealTime Tomography, LLC, PA) will be used for near real-time reconstruction and display of the images.

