1.4.2 Potential Risks

There is a theoretical risk of loss of confidentiality. The consent, interviews and imaging will be performed in private rooms, and all data will be stored securely to minimize these risks. As with standard chest CT, there is a potential for incidental findings. No incidental findings will be shared as they would be based on experimental, non-FDA approved testing.

Study subjects will be exposed to radiation during participation in this study.

For patients who underwent a clinical chest CT: The s-DCT scan exposes the body to radiation. The estimated additional radiation dose is 30.5 mrem. For comparison, the average person in the United States receives a radiation exposure of 300 mrem per year from natural background source. The additional radiation dose that patients will receive in this study is equal to the radiation everyone receives in 37 days from natural background radiation.

For individuals that will receive a modified CT for TAVR: Additional chest tomosynthesis scan (s-DCT) and CT scan expose the body to radiation. The estimated additional radiation dose is from s-DCT scan is 30.5 mrem. The clinical pre-procedural CT for transcatheter aortic valve replacement (TAVR) will be slightly altered in order to expand the field of view by 6 centimeters. This expanded view exposes patients to slightly higher radiation. The effective radiation dose that patients will receive from added length of the scan 55.5 mrem which is only 2% more than what he/she will receive from the scan without added length. For comparison, the average person in the United States receives a radiation exposure of 300 mrem per year from natural background source. The additional radiation dose from both scans is equal to the radiation everyone receives in 105 days from natural background radiation.

There are unknown risks to a fetus. Pregnancy testing will be performed to exclude pregnancy in women of childbearing potential.

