2 STUDY OBJECTIVE

2.1 Primary Objective

The primary objective of the study is to compare CACS between conventionally acquired non-contrast CT and Gated Stationary Chest Tomosynthesis.

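### Sections 1.4.2 and 7.3 give opposite instructions for a tomosynthesis finding that is both incidental and concerning

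*Combined protocol and SAP*

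**What the plan says.** Section 1.4.2 (Potential Risks) accepts that the study scan may show something unlooked for: "As with standard chest CT, there is a potential for incidental findings". It then sets a rule: "No incidental findings will be shared as they would be based on experimental, non-FDA approved testing". The rule names no recipient and has no exception.

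Section 7.3 (Data and Safety Monitoring Plan) describes an early look at the images: "All studies will be reviewed within 7 days (time is needed to move and reconstruct the acquired images"). Its rule on what follows is: "If there are concerning lesions or indicator is identified, this information will be communicated to the referring surgeon", with the primary physician as the alternative recipient. It makes no exception for incidental findings.

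Two other places bear on the point. Section 1.4 says that the research images are not read for decisions about the patient's care. Section 3.1 says that study results will have no effect on care. Neither mentions the 7-day review or says what to do with a worrying lesion.

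**The concern.** For one class of finding the plan gives two instructions that cannot both be carried out. If the 7-day review of an s-DCT scan shows a lesion that is incidental and also concerning, such as one outside the coronary arteries, section 7.3 tells staff to pass it to a physician. Section 1.4.2 tells them that it will not be shared.

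What is at stake is the handling of individual participants, not the statistics. Section 7.3 is the only place that provides for a timely look at each participant's images and for passing on what is seen. There is no follow-up (section 4.3) and no data and safety monitoring board. The medical monitor's stated remit is adverse events and unanticipated problems. The later reader study uses de-identified images.

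**Working it through.** No figure in the plan depends on this point, so the check sets the sections side by side.

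**Step 1: does the 7-day review cover the s-DCT images?** Section 7.3 applies to all studies and explains the interval by the time needed to move and reconstruct images. Reconstruction is mentioned in two other places in the available text, and both concern s-DCT:
- Section 1.3, on the s-DCT computer station: "will be used for near real-time reconstruction and display of the images".
- Section 3.1, on the gated s-DCT scan: "Images will be reconstructed off-line and transferred for review on conventional PACS workstations".

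The review is therefore not confined to the clinical CT.

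**Step 2: could the review be the reader study?** No. Section 3.1 says: "A reader study will be performed after all patients have been accrued". A review within 7 days is a separate activity.

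**Step 3: do the two rules overlap?** Section 1.4.2 governs incidental findings, and section 7.3 governs a concerning lesion or indicator. Neither term is defined. The possible cases for an s-DCT finding are:

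| Finding | Section 1.4.2 | Section 7.3 | Result |
|---|---|---|---|
| Incidental, not concerning | Not shared | Silent | No conflict |
| Concerning, not incidental | Silent | Communicated | No conflict |
| Incidental and concerning | Not shared | Communicated | Conflict |

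The second row may include a concerning coronary calcium result, since calcium is the study's target: "The primary objective of the study is to compare CACS between conventionally acquired non-contrast CT and Gated Stationary Chest Tomosynthesis". Such a result is not claimed as part of the conflict. The third row is not ruled out by the text: section 1.4.2 expects incidental findings, draws the comparison with chest CT in general, and does not limit them to harmless ones.

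**Step 4: does anything else in the available text settle the third row?** No.
- Sections 1.4 and 3.1 lean towards section 1.4.2 and leave section 7.3 unexplained. Section 1.4 does not expressly forbid passing on something noticed, so it is in tension with section 7.3 without contradicting it outright.
- Section 6.3 does not expect tomosynthesis to show lesions absent from the reference standard. That is an expectation attached to an exploratory sensitivity and specificity analysis, not a disclosure rule.

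**Step 5: size.**
- Images under section 7.3: 20 planned participants (sections 3.1 and 3.2), all studies reviewed, so 20 of 20. Sections 6.3 and 6.4 say at least 20. This counts scans reviewed, not participants affected.
- Number with a finding in the third row: not given in the documents.
- Interval between clinical CT and s-DCT: 4 × 7 = 28 days (sections 3.1 and 3.2.1), or up to 28 + 7 = 35 days (sections 3.2 and 4.2).

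**The case against.** The strongest reply is that section 1.4.2 addresses risks to subjects, so *shared* may mean returned to the participant, while section 7.3 names only physicians. On that reading both rules can be followed. The reading is possible, and the text neither states nor excludes it. It fits poorly with the reason given in section 1.4.2, however, because the experimental status of the test applies equally to a physician. Staff should not have to infer the recipient.

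A second reply is that the overlap is narrow and its consequences small. The terms are undefined, target calcium may fall outside section 1.4.2, every participant also has a clinical CT, and section 6.3 expects no lesions beyond the reference standard. This stands as a limit on impact: s-DCT may often not be the only source of a concerning lesion. It does not tell staff what to do when such a lesion is seen.

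A third reply is that the consent form might state who receives findings. Consent pages were not available for this review, and their absence is not held against the plan. Consent wording could clarify what was intended, but it would not correct protocol text that gives two answers.

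**Conclusion.** The concern holds. For an s-DCT finding that is both incidental and concerning, sections 1.4.2 and 7.3 conflict as worded, and nothing in the available text reconciles them. Because the conflict decides whether a participant's physician learns of a concerning lesion, it must be fixed even though it touches neither the sample size nor the primary analysis.

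The conclusion rests on two readings of the text: that the 7-day review includes s-DCT images, which the reconstruction wording supports, and that section 1.4.2 means what it says in naming no recipient. The s-DCT images of all 20 planned participants fall under the review, but the number affected by the conflict is unknown.

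**What to change.** Replace the two statements in sections 1.4.2 and 7.3 with one rule that states:

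- whether s-DCT images are reviewed before the reader study;
- which findings are covered, with *incidental* and *concerning* defined, and whether target coronary calcium counts;
- whether findings are communicated and to whom: participant, physician, both or neither.

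Then align the wording of section 1.4 with that rule and check the consent form against it. Which rule to adopt is for the investigators and the IRB, and this review does not propose one.

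The cost is a short amendment to two sections, a wording check of a third, and a check of the consent form. Scans, sample size and analysis do not change.
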